## 9.2.1 Drug Induced Liver Injury (DILI)

Total bilirubin level should be checked for any subject with increased ALT or AST levels  $\geq$  three times the upper normal limits (ULN) or baseline.

- Reporting all DILI as SAE to the FDA based on Hy's Law:
  - $\Box$  AST or ALT  $\geq$  3 x ULN or baseline and
  - $\Box \quad T_Bili \ge 2 \text{ x ULN or baseline}$

A separate incidence table will be provided for DILI cases, and the corresponding listing will be provided for Safety Sample during the open-label treatment period.

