3.7.4.2 Clinical Laboratory Assessments

A central laboratory designated by the sponsor will be used for all laboratory testing required during the trial. The central laboratory should be used for all laboratory testing whenever possible (including unscheduled and follow-up, if needed). In cases where an immediate result is required for a particular laboratory test, the sample should be divided and sent to both a local laboratory and the designated central laboratory. Urine will be collected and blood will be drawn from each subject prior to treatment with the IMP. Subjects should be fasting for a minimum of 8 hours prior to the blood draws, if possible. If fasting blood samples are not feasible, non-fasting blood samples may be obtained initially for determining eligibility for the trial. A fasting blood sample is required at baseline prior to dosing. Clinical laboratory tests at other visits should be drawn fasting, if possible, but must be drawn after a minimum 8-hour fast at Week 52/ET. Vital sign measurements and ECG assessments should be completed before any blood samples are

Confidential - Proprietary Information

61

collected. See exclusion criteria (Section 3.4.3) for laboratory tests. For de novo subjects, if a fasting blood sample was obtained at the screening visit and less than 14 days have elapsed since the screening visit, clinical laboratory tests (hematology, serum chemistry, and urinalysis) do not need to be repeated at the baseline visit. The results of these tests must be reviewed by the investigator prior to initiation of the administration of the IMP. Additional urine and blood samples may be collected for further evaluation of safety as warranted by the investigator's judgment. Reports from the central laboratory will be retained electronically within the lab vendor's online portal and assessed by the investigator or qualified designee for clinical significance within eCRF.

Confidential - Proprietary Information

| Table 3.7.4.2-1 Clinical Laboratory Assessments | | | | |
|---|---|--|--|--|
| Hematology: | Serum Chemistry: | | | |
| Hematocrit | Albumin | | | |
| Hemoglobin | Alkaline phosphatase | | | |
| Mean corpuscular hemoglobin concentration | ALT | | | |
| Mean corpuscular hemoglobin | AST | | | |
| Mean corpuscular volume | Bicarbonate | | | |
| Platelet count | Bilirubin, total | | | |
| RBC count | Blood urea nitrogen | | | |
| WBC count with differential | Calcium | | | |
| | Cholesterol (total, HDL, LDL) | | | |

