5.1 Definitions

An AE is defined as any untoward medical occurrence in a patient or clinical trial subject administered a medicinal product and which does not necessarily have a causal relationship with this treatment. The AEs would not include information recorded as medical history at screening for preplanned procedures for which the underlying condition was known and no worsening occurred. An adverse reaction is any untoward and unintended response to an IMP-related to any dose administered.

A suspected adverse reaction is any AE for which there is a reasonable possibility that the IMP caused the AE. For the purpose of Investigational New Drug (IND) safety reporting, "reasonable possibility" means there is evidence to suggest a causal relationship between the IMP and the AE. Suspected adverse reaction implies a lesser degree of certainty about causality.

An SAE includes any event that results in any of the following outcomes:

- Death
- Life-threatening; ie, the subject was, in the opinion of the investigator, at immediate risk of death from the event as it occurred. It does not include an event that, had it occurred in a more severe form, might have caused death.
- Persistent or significant incapacity/disability or substantial disruption of the ability to conduct normal life functions.
- Requires in-patient hospitalization or prolongs hospitalization.
 - Hospitalization itself should not be reported as an SAE; whenever possible the reason for the hospitalization should be reported.
 - Hospitalizations or prolonged hospitalizations for social admissions (ie, those required for reasons of convenience or other non-medical need) are not considered SAEs.
- Congenital anomaly/birth defect.
- Other medically significant events that, based upon appropriate medical judgment, may jeopardize the subject and may require medical or surgical intervention to prevent one of the outcomes listed above; eg, allergic bronchospasm requiring intensive treatment in an emergency room or home, blood dyscrasias or convulsions that do not result in hospitalization, or the development of drug dependency or drug abuse.

Nonserious adverse events are all AEs that do not meet the criteria for a "serious" AE.

Immediately Reportable Event:

- Any SAE.
- Any AE of special interest (AESI) (see Section 5.4)
- Any AE related to occupational exposure.
- Potential serious hepatotoxicity (see Section 5.6).

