5.3 Immediately Reportable Events

The investigator must immediately report after either the investigator or site personnel become aware of any SAE, AE related to occupational exposure, AESI, potential serious hepatotoxicity, or confirmed pregnancy, by telephone, fax, or e-mail to the sponsor using the contact information on the cover page of this protocol. An IRE form must be completed and sent by e-mail, fax, or overnight courier to the sponsor (Please note that the IRE form is NOT the AE eCRF).

Subjects experiencing SAEs should be followed clinically until their health has returned to baseline status, or until all parameters have returned to normal or have otherwise been explained. It is expected that the investigator will provide or arrange appropriate supportive care for the subject and will provide prompt updates on the subject's status to the sponsor.

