5.6 Potential Serious Hepatotoxicity

For a subject who experiences an elevation in aspartate aminotransferase (AST) or alanine aminotransferase (ALT) that is ≥ 3 times the upper limit of normal (ULN), a total bilirubin level should also be evaluated. If the total bilirubin is ≥ 2 times the ULN, complete an IRE form with all values listed and also report as an AE on the eCRF.

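### SAP 9.2.1 adds an undefined baseline alternative to both Hy's Law limits, where protocol 5.6 uses ULN only, so the DILI table can count a different set of cases from the protocol's

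*SAP*

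**What the plan says.** SAP 9.2.1 begins with a monitoring instruction, "Total bilirubin level should be checked for any subject with increased ALT or AST levels" of at least three times ULN or baseline. It then has a line that starts "Reporting all DILI as SAE to the FDA based on" Hy's Law, with two conditions below it. The first is AST or ALT at or above "3 x ULN or baseline and" the second is total bilirubin at or above 2 x, again against ULN or baseline. The section closes with the analysis: "A separate incidence table will be provided for DILI cases", plus a listing, in the Safety Sample over the open-label period. It gives no other definition of a case. The outputs are most likely CT-10.4.1 and CT-10.4.2 in SAP section 12, although those titles speak only of potentially liver-injury-related laboratory abnormalities.

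Protocol 5.6 uses 3 x ULN for AST or ALT and 2 x ULN for total bilirubin, with no baseline alternative. When both are met the site is to "complete an IRE form with all values listed and also report as an AE on the eCRF". The AST and ALT criteria in SAP Appendix 2 are also against ULN only, and its total bilirubin criterion is a fixed 2.0 mg/dL. SAP 7.1 defines baseline as the last available value before the first open-label dose, so baseline may lie anywhere in the normal range, or above it.

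**The concern.** A Hy's Law count is read as a signal of serious liver injury, and safety is the primary objective of this trial. The SAP's case rule differs from the protocol's and leaves open how ULN and baseline combine. A programmer would have to choose, and the possible choices move the case set in opposite directions.

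One choice admits subjects whose liver tests never left the normal range. Such a subject would have no AST, ALT or bilirubin entry in the clinical-relevance tables, whereas every case under the ULN-only rule meets at least the Appendix 2 AST or ALT limit. The other choice can leave out a subject who started with raised values and who meets the protocol's definition.

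**Working it through.** The plan gives no figure to reproduce. The check compares the rules as written and then sizes the lower-of reading under stated assumptions.

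**1. The rules in units of ULN, with baseline B.**
- Protocol 5.6: AST or ALT >= 3, and bilirubin >= 2.
- SAP, lower-of: AST or ALT >= min(3, 3B), and bilirubin >= min(2, 2B). This differs from the protocol only if B < 1.
- SAP, higher-of: AST or ALT >= max(3, 3B), and bilirubin >= max(2, 2B). This differs only if B > 1.

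| Baseline (x ULN) | ALT/AST lower-of | ALT/AST higher-of | Bilirubin lower-of | Bilirubin higher-of |
|---|---|---|---|---|
| 0.33 | 1.0 | 3.0 | 0.67 | 2.0 |
| 0.50 | 1.5 | 3.0 | 1.0 | 2.0 |
| 0.75 | 2.25 | 3.0 | 1.5 | 2.0 |
| 1.0 | 3.0 | 3.0 | 2.0 | 2.0 |
| 2.0 | 3.0 | 6.0 | 2.0 | 4.0 |

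**2. When a wholly normal subject can be a case (lower-of).** The condition is 3B <= 1 for ALT or AST and 2B <= 1 for bilirubin, that is, baselines at or below ULN/3 and ULN/2. Worked case, with assumed ULN of 40 U/L and 1.2 mg/dL: ALT goes from 12 to 36 (3 x 12 = 36) and bilirubin from 0.3 to 0.6 (2 x 0.3 = 0.6). Both SAP limits are met and both values are normal. Protocol 5.6 would need 120 U/L and 2.4 mg/dL. On the higher-of reading this subject is not a case.

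**3. Where the higher-of reading acts.** Entry excludes AST or ALT only above 2 x ULN (protocol Tables 3.4.3.1-1 and 3.4.3.2-1), so a baseline of 2 x ULN is allowed. The trigger there is 3 x 2 = 6 x ULN, against the protocol's 3 x ULN.

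**4. Illustrative size (lower-of, no drug effect, per 720 subjects).** The documents give no ULN, no within-subject CV and no baseline distribution, so everything below except the visit schedule and exposure targets is assumed.
- Draws: chemistry is taken at Weeks 8, 26, 38 and 52/ET. Retention is piecewise exponential through the protocol 3.3.1 targets, 300/720 at Week 26 and 100/720 at Week 52. That gives (300/720)^(8/26) = 0.76 at Week 8, 0.42 at Week 26 and 0.42 x (100/300)^(12/26) = 0.25 at Week 38. With one Week 52/ET draw each, mean post-baseline draws are 1 + 0.76 + 0.42 + 0.25 = 2.43.
- Values: lognormal, medians 20 U/L (ALT, AST) and 0.5 mg/dL, and between-subject log SD 0.40. The AST-ALT correlation is 0.6 between and 0.5 within subjects, and bilirubin is independent. Baseline AST and ALT are at most 2 x ULN, with the ULNs in step 2.

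| Common within-subject CV | Wholly normal cases, limits met on any draws | Wholly normal cases, same draw |
|---|---|---|
| 20% | 0.00 | 0.00 |
| 25% | 0.07 | 0.03 |
| 30% | 0.5 | 0.3 |
| 35% | 1.8 | 0.9 |

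The ULN-only rule gives under 0.03 expected cases in each of these settings. With separate CVs for transaminases and bilirubin (any draws), wholly normal cases are 0.01 at 20%/35%, 0.17 at 25%/35%, 0.75 at 30%/35% and 0.7 at 35%/25%.

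**5. Sensitivity to the medians (any draws, CV 30% and 35%).** A bilirubin median of 0.7 mg/dL lowers the wholly normal counts to 0.35 and 1.2. Raising the ALT/AST median to 24 U/L as well lowers them to 0.24 and 0.79. All lower-of cases, including those with some value above ULN, do not fall: they stay at about 1.4 to 1.6 and 5.2 to 5.8.

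**The case against.** The strongest reply is that the clause has a sensible purpose. Entry permits AST and ALT up to 2 x ULN, so some subjects start above normal, and the wording may be shorthand for ULN, or baseline where baseline is already raised. On that reading no all-normal subject is a case. This stands as a plausible intention, but SAP 9.2.1 does not state it, and it would still depart from protocol 5.6 by raising the trigger.

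A second reply is that the effect is small and visible. The listing covers the same cases, the probable table titles describe a laboratory screen and not adjudicated Hy's Law, and ULN-based AST and ALT incidence is tabulated separately. This also stands in part: a reader of the listing could spot a wholly normal case. The incidence figure would still include it.

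A third reply is that the sizing rests on assumed inputs. That is correct. The retention curve also treats exposure targets that protocol 3.3.1 words as a minimum as if they were estimates.

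A reader might infer something stronger, that the multiplier applies to ULN alone and any value at or above baseline qualifies. The documents do not support that. The opening sentence of SAP 9.2.1 speaks of increased levels of three times ULN or baseline. An increased level already exceeds baseline, so a bare baseline arm would add nothing. The multiplier is best taken to govern both terms.

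**Conclusion.** The discrepancy is certain. SAP 9.2.1 puts a baseline alternative into both limits, protocol 5.6 has none, and the SAP does not say how the two references combine. Either reading can give a case set different from the protocol's.

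The numerical effect is not certain. Under the assumptions above, the lower-of reading adds nothing of note if the transaminase CV is 20% or lower, and about one or two wholly normal subjects per 720 at a CV of 35%. The ULN-only rule expects essentially zero cases, so a single such subject could be the whole reported incidence. The effect of the higher-of reading was not sized, because the documents do not say how many subjects have raised baselines.

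A reader might infer that a false liver signal is to be expected, or that it would be hidden. The documents support neither. The count may well be zero, and the planned listing would expose a spurious case.

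**What to change.** **Analysis.** Give the case definition for the DILI incidence table and listing in its own sentence in SAP 9.2.1, using the protocol 5.6 limits (AST or ALT at least 3 x ULN and total bilirubin at least 2 x ULN). State whether both must be met on the same draw, which the section now leaves open. If baseline-relative rises are of interest, show them in a separate table that carries neither the Hy's Law nor the DILI label, and define how baseline enters.

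**Safety reporting.** The sponsor should reconcile SAP 9.2.1 with protocol 5.1, 5.3 and 5.6. The protocol already sends both SAEs and potential serious hepatotoxicity by the same route ("An IRE form must be completed and sent by e-mail, fax, or overnight courier to the sponsor"). The open points are therefore the trigger and the automatic SAE status that SAP 9.2.1 adds. This point does not say which reporting rule is right. The difference in the bilirubin-check trigger has little effect on scheduled data, because "Bilirubin, total" is in the routine chemistry panel (protocol Table 3.7.4.2-1).

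**Cost.** A wording change in the SAP and one derivation. No new data are needed.

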## 9.3 Physical Examination and Vital Signs

Summary statistics for changes from baseline in vital signs will be provided for the Safety Sample. By-patient listings will be provided for physical examination.

Potentially clinically relevant vital signs measurements identified in the open-label treatment phase for the Safety Sample will be listed and summarized. Criteria for identifying vital signs of potential clinical relevance are provided in Appendix 1.

In addition, the change from baseline in weight, BMI, and waist circumference, and potentially clinically relevant abnormalities in weight, will also be summarized.

#### 9.4 Electrocardiogram (ECG) Data

Summary statistics and incidence of potentially clinically relevant changes will be provided for ECG parameters.

For the analysis of QT and QTc, data from three consecutive complexes (representing three consecutive heart beats) will be measured to determine average values. The following QT corrections will be used for reporting purposes in the clinical study report:

- QTcB is the length of the QT interval corrected for heart rate by the Bazett formula: QTcB=QT/(RR)0.5 and
- QTcF is the length of the QT interval corrected for heart rate by the Fridericia formula: QTcF=QT/(RR)0.33
- QTcN is the length of the QT interval corrected for heart rate by the FDA Neuropharm Division formula: QTcN=QT/(RR)0.37

Potentially clinically relevant changes in the 12-lead ECG identified in the open-label treatment phase for the Safety Sample will be listed and summarized. Criteria for identifying ECG measurements of potential clinical relevance are provided in Appendix 3.

Categorical changes in ECG parameters during the open-label treatment period will be summarized based on the following criteria:

Categorical Change Criteria in QT/QTc Parameters				
Classification Category		Criteria		
QT	New Onset (> 450 Msec)	New onset (>450 msec) in QT means a subject who attains a value > 450 msec during treatment period but not at baseline.		
QTc *	New Onset (> 450 Msec)	New onset (> 450 msec) in QTc means a subject who attains a value > 450 msec during treatment period but not at baseline.		
	New Onset (> 450 Msec) And > 10% Increase	New onset (> 450 msec) and > 10% increase in QTc means a subject who attains a value > 450 msec and > 10% increase during treatment period but not at baseline		
	New Onset (> 500 Msec)	New onset (> 500 msec) in QTc means a subject who attains a value > 500 msec during treatment period but not at baseline.		
	Increase 30 - 60 Msec	Increase from baseline value > 30 and $\leq$ 60 msec in QTc		
	Increase > 60 Msec	Increase from baseline value > 60 msec in QTc		

\* QTc categorical change criteria apply to QTcB, QTcF and QTcN.

#### 9.5 Suicidality Data

Suicidality will be monitored during the study using the C-SSRS and will be summarized as number and percentage of subjects reporting any suicidal behavior, ideation, behavior by type (4 types), ideation by type (5 types) and treatment emergent suicidal behavior and ideation. Summary will be provided for the open-label treatment period for the Safety Sample.

Suicidality is defined as report of at least one occurrence of any type of suicidal ideation or at least one occurrence of any type of suicidal behavior during assessment period (count each person only once).

Treatment emergent suicidal behavior and ideation is summarized by four types: Emergence of suicidal ideation, Emergence of serious suicidal ideation, Worsening of suicidal ideation, Emergence of suicidal behavior.

Emergence of suicidal behavior/ideation is defined as report of any type of suicidal behavior/ideation during treatment when there was no baseline suicidal behavior/ideation.

Emergence of serious suicidal ideation is defined as observation of suicidal ideation severity rating of 4 or 5 during treatment when there was no baseline suicidal ideation.

Worsening of suicidal ideation is defined as a suicidal ideation severity rating that is more severe than it was at baseline.

For the open-label treatment period analyses, the last available measurement prior to the first dose of open-label IMP is being used as "Baseline".

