| 6. | Following responses from the "Since Last Visit" version of the C-SSRS 7-day follow-up visit of double-blind pahse 3 trial, (ie, Trial 405-201-00013 or Trial 405-201-00014): Subjects with a response of "Yes" on the C-SSRS Suicidal Ideation Item 4 (Active Suicidal Ideation with Some Intent to Act, Without Specific Plan) at entry, OR Subjects with a response of "Yes" on the C-SSRS Suicidal Ideation Item 5 (Active Suicidal Ideation with Specific Plan and Intent) at entry, OR Subjects with a response of "Yes" on any of the 5 C-SSRS Suicidal Behavior Items (actual attempt, interrupted attempt, aborted attempt, preparatory acts, or behavior) at entry, |
| | OR Subjects who, in the opinion of the investigator (including consideration of responses on the C-SSRS throughout Trial 405-201-00013 or Trial 405-201-00014), present a serious risk of suicide. Note: "Entry" is defined as the 7-day follow-up of Trial 405-201-00013 or Trial 405-201-00014. |
| 7. | Subjects with newly developed psychiatric or medical condition that would be exclusionary under the criteria listed for Trial 405-201-00013 or Trial 405-201-00014. |
| 8. | Subjects that have a positive alcohol test (via breathalyzer or blood), a positive drug screen for cocaine, or other illicit drugs (excluding marijuana). Subjects with a positive drug screen for confirmed prescription medications at baseline will not be permitted to continue participation in Trial 405-201-00015. NOTE: Subjects that test positive for marijuana may be permitted to be enrolled if they have no evidence of a substance use disorder, and if they agree to refrain from use for the duration of the trial. Allowance for subjects testing positive for marijuana at screening require explicit approval from the medical monitor. |
| 9. | Any new or developing safety concerns related to vital signs in the opinion of the investigator during the baseline visit. |

Confidential - Proprietary Information

| Tabl | e 3.4.3.1-1 Exclusion Criteria for Rollover Subjects from |
|-------|---|
| | Trial 405-201-00013 or Trial 405-201-00014 |
| 10. | The following laboratory test and ECG results are exclusionary: |
| | 1) Platelets \leq 75,000/mm ³ |
| | 2) Hemoglobin $\leq 9 \text{ g/dL}$ |
| | 3) Neutrophils, absolute $\leq 1000/\text{mm}^3$ |
| | 4) AST > $2 \times$ upper limit of normal |
| | 5) ALT > 2 × upper limit of normal |
| | 6) Creatinine $\geq 2 \text{ mg/dL}$ |
| | 7) HbA ₁ c \geq 7% |

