| 5. | Following responses from the "Since Last Visit" version of the C-SSRS (subjects should reference their last visit on Trial 405-201-00013 or Trial 405-201-00014): Subjects with a response of "Yes" on the C-SSRS Suicidal Ideation Item 4 (Active Suicidal Ideation with Some Intent to Act, Without Specific Plan) at entry, OR Subjects with a response of "Yes" on the C-SSRS Suicidal Ideation Item 5 (Active Suicidal Ideation with Specific Plan and Intent) at entry, OR Subjects with a response of "Yes" on any of the 5 C-SSRS Suicidal Behavior Items (actual attempt, interrupted attempt, aborted attempt, preparatory acts, or behavior) at entry, OR Subjects who, in the opinion of the investigator (including consideration of responses on the C-SSRS throughout Trial 405-201-00013 or Trial 405-201-00014), present a serious risk of suicide. |
| 6. | Subjects with a newly developed psychiatric or medical condition that would be exclusionary under the criteria listed for Trial 405-201-00013 or Trial 405-201-00014. |
| 7. | Subjects that have a positive alcohol test (via breathalyzer or blood), or a positive drug screen for cocaine or other illicit drugs (excluding marijuana). Subjects with a positive drug screen for confirmed prescription medications at baseline will not be permitted to continue participation in Trial 405-201-00015. NOTE: Subjects that test positive for marijuana may be permitted to be enrolled if they have no evidence of a substance use disorder, and if they agree to refrain from use for the duration of the trial. Allowance for subjects testing positive for marijuana at screening requires explicit approval from the medical monitor. |
| 8. | Any new or developing safety concerns related to vital signs in the opinion of the investigator during the baseline visit. |

Confidential - Proprietary Information

14

| Tabl | Table 3.2-1 Exclusion Criteria for Late Rollover Subjects From Trial 405 201 00013 or Trial 405 201 00014 | | | | | | |
|-------|--|--|--|--|--|--|--|
| | 1 mai 405-201-00015 of 1 mai 405-201-00014 | | | | | | |
| 9. | The following laboratory test and ECG results are exclusionary: | | | | | | |
| | 1) Platelets $\leq 75000/\text{mm}^3$ | | | | | | |
| | 2) Hemoglobin $\leq 9 \text{ g/dL}$ | | | | | | |
| | 3) Neutrophils, absolute $\leq 1000/\text{mm}^3$ | | | | | | |
| | 4) AST > $2 \times$ upper limit of normal | | | | | | |
| | 5) ALT > 2 \times upper limit of normal | | | | | | |

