#### 12 Proposed List of Summary Tables

- CT-1.1 Subject Disposition (Enrolled Sample)
- CT-1.2 Subject Disposition by Center (Enrolled Sample)
- CT-1.3 Subject Completion Rates by Week (Enrolled Sample)
- CT-1.4.1 Subject Enrollment by Country (Enrolled Sample)
- CT-1.4.2 Subject Enrollment by Country by Age Group (Enrolled Sample)
- CT-1.5 Summary of Proportion of Face-to-Face and Virtual Visits by Study Week (Enrolled Sample)
- CT-2 Reasons for Discontinuation (Enrolled Sample)
- CT-3.1 Demographic Characteristics (Enrolled Sample)
- CT-3.2.1 Medical History (Enrolled Sample)
- CT-3.2.2 Psychiatric History (Enrolled Sample)
- CT-3.2.3 Summary of Adult ADHD Clinical Diagnostic Scale (ACDS) (Enrolled Sample)
- CT-3.3 MINI International Neuropsychiatric Interview (M.I.N.I.) (Enrolled Sample)
- CT-3.4.1 Baseline Psychiatric Scale Evaluations (Enrolled Sample)
- CT-4.1.1 Concomitant Medications: Medications Taken Prior to Start of Study Therapy (Safety Sample)
- CT-4.1.2 Concomitant Medications: Medications Taken During Study Therapy (Safety Sample)
- CT-4.1.3 Concomitant Medications: Medications Taken Post Study Period (Safety Sample)
- CT-5.1.1 Summary of Mean Change from Baseline in Adult ADHD Investigator Symptom Rating Scale (AISRS) Total Score (Efficacy Sample)
- CT-5.1.2 Summary of Mean Change from Baseline in Adult ADHD Investigator Symptom Rating Scale (AISRS) Total Score by Visit Type (Efficacy Sample)
- CT-5.2 Summary of Mean Change from Baseline in AISRS Inattentive Subscale (Efficacy Sample)
- CT-5.3 Summary of Mean Change from Baseline in AISRS Hyperactive-Impulsive Subscale (Efficacy Sample)
- CT-5.4 Summary of Mean Change from Baseline in Clinical Global Impression Severity of Illness Modified for ADHD (CGI-S) Scale (Efficacy Sample)
- CT-5.5.1 Summary of Mean Change in Attention-Deficit Hyperactivity Disorder Impact Module Adult (AIM-A) Scale (Efficacy Sample)
- CT-5.5.2 Summary of Proportion of Subjects in Each Category in Attention-Deficit Hyperactivity Disorder Impact Module - Adult (AIM-A) Scale (Efficacy Sample)

- CT-6.1 Columbia-Suicide Severity Rating Scale(C-SSRS), Suicidality (Safety Sample)
- CT-6.2 Columbia-Suicide Severity Rating Scale(C-SSRS), Suicidal Behavior by Type (Safety Sample)
- CT-6.3 Columbia-Suicide Severity Rating Scale(C-SSRS), Suicidal Ideation by Type (Safety Sample)
- CT-6.4 Columbia-Suicide Severity Rating Scale(C-SSRS), Treatment Emergent Suicidal Behavior and Ideation (Safety Sample)

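### The suicidality exclusion is stated in conflicting ways for de novo subjects; separately, the SAP 9.5 serious-ideation row leaves out escalation from baseline ratings 1–3

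*SAP*

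**What the plan says.** **Exclusion.** The rule appears in several places.

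- Protocol Table 3.4.3.2-1, exclusion 7 (de novo, Baseline/Screening form): ideation items 4 or 5 in the past 6 months, or a behavior item whose latest episode was in the past 2 years.
- Protocol Table 3.4.3.1-1, exclusion 6 (rollover): responses at the parent trial's 7-day follow-up. It bars a positive "C-SSRS Suicidal Ideation Item 4 (Active Suicidal Ideation with Some Intent to Act, Without Specific Plan) at entry", the corresponding item 5, any behavior item, or serious risk in the investigator's opinion. It has no 30-day or 1-year window.
- COVID-19 Addendum Table 3.2-1, exclusion 5 (late rollover): the same items, for example "C-SSRS Suicidal Ideation Item 5 (Active Suicidal Ideation with Specific Plan and Intent) at entry".
- Protocol 3.7.4.6.2: active ideation in the preceding 30 days, behavior in the preceding year, or serious risk in the investigator's judgment. It refers the reader to Tables 3.4.3.1-1 and 3.4.3.2-1. SAP 10.2.5 repeats the rule without the table references.

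**Reporting.** SAP 9.5 plans summaries of "ideation by type (5 types) and treatment emergent suicidal behavior and ideation". Its category for emergence of serious ideation is "observation of suicidal ideation severity rating of 4 or 5 during treatment when there was no baseline suicidal ideation". General emergence also requires none at baseline. Worsening is "a suicidal ideation severity rating that is more severe than it was at baseline", with no threshold at 4. For baseline, "the last available measurement prior to the first dose of open-label IMP is being used as" the reference. SAP 12 plans CT-6.3 (ideation by type), CT-6.4 (the treatment-emergent categories), CT-6.7 (listing of serious emergence) and CT-6.8 (listing of worsening).

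**The concern.** On the exclusion, one safety rule for entry carries two sets of look-back windows, and the text section cites tables that do not contain its windows. The same history can fall inside one wording and outside the other.

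On reporting, the numbered entry criteria bar items 4 and 5 but not ratings 1–3. A subject with mild baseline ideation who reaches intent or plan on treatment is then in neither emergence category. A reader who takes the serious-emergence row, or CT-6.7, as the full set of subjects newly at 4 or 5 would have to consult CT-6.3 and CT-6.8 to find the rest. The SAP treats a threshold differently elsewhere. In SAP 9.4, new-onset QTc above 500 msec requires only that the threshold was not exceeded at baseline, so a change from 480 to 510 counts.

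The two points are linked, because the exclusion wording that governs affects who can have a nonzero baseline rating.

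**Working it through.** **1. Exclusion wordings side by side (de novo subjects).**

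| History | Exclusion 7 as printed | Windows in Protocol 3.7.4.6.2 / SAP 10.2.5 | Other route to exclusion |
|---|---|---|---|
| Behavior 18 months ago | inside (18 ≤ 24 months) | outside (18 > 12 months) | investigator-judgment limb of the text |
| Item 4 or 5 three months ago | inside (3 ≤ 6 months) | outside (more than 30 days) | investigator-judgment limb of the text |
| Active ideation below item 4, ten days ago | outside its ideation items | inside (10 ≤ 30 days) | exclusions 8 and 25 |

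The behavior windows differ by 24 − 12 = 12 months. No difference is computed for ideation, because one wording names items 4 and 5 and the other names active ideation. The documents do not say which of ratings 1–3 count as active, so the third row applies only to a rating that does. The table reaches further back, while the text may reach lower ratings.

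**2. SAP 9.5 applied to each change in rating.** Inputs: baseline rating b from 0 to 3, since the numbered criteria bar items 4 and 5, and worst on-treatment rating t. The plan gives no figure to reproduce.

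- Ways to reach t = 4 or 5: 4 × 2 = 8.
- Counted as serious emergence (b = 0): 1 × 2 = 2.
- Not counted there (b = 1, 2 or 3): 3 × 2 = 6. All 6 meet Worsening; none meets general emergence of ideation.
- If the 30-day text bars k of the ratings 1–3 at entry, the number not counted is 2 × (3 − k): 6, 4, 2 or 0 for k = 0, 1, 2 or 3.

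SAP 9.5 does not say whether Worsening needs a baseline rating of at least 1.

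- If it does: 4 + 3 + 2 = 9 upward changes, of which 6 reach 4 or 5 and 3 are lesser rises.
- Read literally, with rises from 0 included: 9 + 5 = 14, of which 8 reach 4 or 5 and 6 are lesser rises.

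These are kinds of change, not subjects, and they are not equally likely. They show what the definition covers and do not measure how many subjects are affected.

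**The case against.** On reporting, the SAP scheme is coherent on its own terms: emergence means from none, and a rise from an existing rating is Worsening. Nothing in the documents requires otherwise, so the row is correct under its own definition. CT-6.3 gives types 4 and 5 separately; with those items barred at entry, its rows already show nearly all subjects newly at 4 or 5. CT-6.8 lists the rises. The affected group is also narrow. Baseline is one pre-dose rating, normally the Since Last Visit form at Day −1 or at the parent trial's 7-day follow-up, so ideation reported only at de novo screening does not count. CT-6.7 is known only by its title. All of this stands. What remains is that CT-6.3 is a count that does not show baseline, and Worsening mixes escalation to 4 or 5 with smaller rises.

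On the exclusion, Protocol 3.4.3.2 makes the table the operative list, and Protocol 3.7.4.6.2 sends the reader to it. Investigator judgment can exclude a subject under either wording. Exclusion 7 also ends on a dangling OR in the available text, so a further limb may be missing. These points limit the consequence, but the printed windows still conflict, whatever a missing limb might say.

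**Conclusion.** The exclusion is wrong as written. Its windows disagree (6 months versus 30 days for differently described ideation; 2 years versus 1 year for behavior), and the tables cited in Protocol 3.7.4.6.2 do not support that section's windows. A reader might infer that the text would admit subjects whom the table excludes, that one wording is simply stricter, or that no rule exists. The documents support none of these: judgment clauses apply on both sides, the wordings differ in type of ideation as well as in time, and the table is operative. SAP 5.1 ties no analysis sample to this wording.

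The SAP 9.5 point is a near-free improvement. A reader might infer that serious ideation is lost or undercounted, or take 6 of 8 as a 75% miss. Neither follows: the cases appear under Worsening and by type, and the documents give no frequency of baseline ratings 1–3. The number of subjects cannot be derived and may be zero. This rests on CT-6.7 following the SAP 9.5 definition, and on baseline ratings of 4 or 5 not being enrolled.

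**What to change.** **Exclusion.** Reconcile Table 3.4.3.2-1 exclusion 7, Protocol 3.7.4.6.2 (including its reference to Table 3.4.3.1-1) and SAP 10.2.5 to one rule. Which rule is a clinical decision outside this review. The cost is a wording change in both documents.

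**Reporting.** In SAP 9.5, define emergence of serious suicidal ideation as an on-treatment rating of 4 or 5 with a baseline rating of 0–3, keeping the last pre-dose baseline, and apply it to CT-6.4 and CT-6.7. Show the from-zero subset as its own row, so that the present count remains visible. State whether Worsening requires a baseline rating of at least 1, and footnote that a subject can appear in both categories. The cost is one definition line, one extra row and a count that overlaps with Worsening, all from data already collected.
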